4.4.2. Secondary Efficacy Variables

ORR by investigator assessment is determined by the proportion of patients with best overall response of CR or PR based on investigator-assessed evaluation..

Duration of response (DOR) is determined for patients with BOR of CR or PR. DOR is measured from the time measurement criteria are first met for CR/PR (whichever is first recorded) until the first date of recurrent or progressive disease (photographic or radiographic), or death due to any cause.

- Patients who do not have a documented tumor progression or death will be censored at the last evaluable tumor assessment.
- Patients who do not have a documented tumor progression or death before initiation of new anti-cancer therapy will be censored at the last evaluable tumor assessment prior to or on the date of new anti-cancer therapy.
- Patients who do not have any evaluable post-baseline tumor assessment and do not die will be censored on the date of first study treatment.

Progression-free survival (PFS) is measured from the start of treatment until the first date of recurrent or progressive disease (photographic or radiographic), or death due to any cause.

- Patients who do not have a documented tumor progression or death will be censored at the last evaluable tumor assessment.
- Patients who do not have a documented tumor progression or death before initiation of new anti-cancer therapy will be censored at the last evaluable tumor assessment prior to or on the date of new anti-cancer therapy.
- Patients who do not have any evaluable post-baseline tumor assessment and do not die will be censored on the date of first study treatment.

Overall survival (OS) is measured from the start of treatment until death due to any cause. Patients who do not die will be censored at the last date that patient is documented to be alive. As many patients may receive new anti-cancer therapy after disease progression, a sensitivity analysis of OS will be conducted by censoring patients at the first date of a new anti-cancer therapy is taken.

Time to tumor response (TTR) is determined for patients with BOR of CR or PR. TTR is measured from the start of treatment until the time measurement criteria are first met for CR/PR (whichever is first recorded).

For all of the above time-to-event variables, the time to event (day) is the date of event/censor - the date of first study treatment + 1.

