5.8.2. Analysis of Secondary Efficacy Variables

ORR derived from the overall response that is based on investigator review will be analyzed similarly as primary efficacy variable.

DOR: The distribution of DOR will be estimated using the Kaplan-Meier method. The median DOR along with its 95% CI will be presented by group and Kaplan-Meier estimates with 2-sided 95% CIs at specific time points (for example, 6, 12, 18 and 24 months) will be summarized. The Kaplan-Meier curves will be displayed by group. DOR will also be summarized descriptively by range. Number and percentage of patients with DOR at specific time periods of interest (e.g., $>=3$ months, $>=6$ months, $>=12$ months, $>=18$ months, etc.) will be summarized by group.

PFS: The distribution of PFS will be estimated using the Kaplan-Meier method. The median PFS along with its 95% CI will be presented by group and Kaplan-Meier estimates with 2-sided 95% CIs at specific time points (for example, 6, 12, 18 and 24 months) will be summarized. The Kaplan-Meier curves will be displayed by group.

OS: The distribution of OS will be estimated using the Kaplan-Meier method. The median OS along with its 95% CI will be presented by group and Kaplan-Meier estimates with 2-sided 95% CIs at specific time points (for example, 6, 12, 18 and 24 months) will be summarized. The Kaplan-Meier curves will be displayed by group. A variant of OS defined by censoring patients at the start date of subsequent therapy will be summarized and displayed by Kaplan-Meier approach as a sensitivity analysis.

TTR will be summarized descriptively by group and at specific time periods of interest (e.g., <2 months, 2 to 4- months, 4 to 6- months, $>=6$ months).

CR rate, DCR and dDCR will be summarized by group and the corresponding 2-sided 95% exact binomial confidence intervals will be derived using the Clopper-Pearson method.

The duration of response and the best percentage change from baseline in target lesions will be presented by swimmer plot and waterfall plot respectively.

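### Applied as written, the SAP's single time-to-event formula starts duration of response at first dose and overstates it by each responder's time to response

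*SAP*

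**What the plan says.** SAP 4.4.2 (Secondary Efficacy Variables) gives DOR its own starting point: "DOR is measured from the time measurement criteria are first met for CR/PR (whichever is first recorded"). It restricts the variable to responders: "Duration of response (DOR) is determined for patients with BOR of CR or PR". PFS, OS and TTR start at treatment; for example, "Progression-free survival (PFS) is measured from the start of treatment until the first date of recurrent or progressive disease", and for TTR, "TTR is measured from the start of treatment until the time measurement criteria are first met for CR/PR (whichever is first recorded").

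After those four definitions, the section gives one calculation rule. Its scope is "For all of the above time-to-event variables", and for these "the time to event (day) is the date of event/censor - the date of first study treatment + 1".

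SAP 5.8.2 then uses DOR in a Kaplan-Meier median, in Kaplan-Meier estimates at fixed times (6, 12, 18 and 24 months are given as examples), in a range, in a swimmer plot, and in a table described as "Number and percentage of patients with DOR at specific time periods of interest", with thresholds such as 3, 6, 12 and 18 months. Neither 5.8.2 nor the data conventions in SAP section 6 give a separate calculation for DOR.

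**The concern.** DOR is the first time-to-event variable above the formula, and the formula makes no exception. The section therefore holds a definition in words that starts at response and a calculation rule that starts at first dose. For every responder the two give different numbers.

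The error has one direction. First response cannot precede first dose, so the formula can only lengthen DOR. It affects the median, the fixed-time estimates, the threshold counts, and the later update of response duration.

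This matters because the trial is single-arm, the SAP calls it pivotal, and DOR is the main support for the response rate. The timing of the primary data cut was chosen so that ORR and DOR could both be described (SAP section 5). Post-treatment follow-up was lengthened by a year after regulatory feedback in order to capture DOR more stringently (SAP 1.2.5). Both documents cite median DOR values of 7.6 and 9.5 months for a previous agent (protocol 1.1, SAP 1.1.1). A shift of two months or more is large on that scale.

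**Working it through.** **Inputs.** Tumor assessments are every 9 weeks in cycles 1–5 and every 12 weeks in cycles 6–9 (protocol 8.2.2). The first is on day 64 ± 3 (protocol Table 4). The minimum follow-up at the primary analysis is about 57 weeks, split into 27 for response and 30 for DOR (SAP section 5). A month is taken as 30.4375 days.

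**The plan's own figure.** Cycles 1–3: 3 × 9 = 27 weeks. Cycles 4–6: 9 + 9 + 12 = 30 weeks. Total 57 weeks, as stated. This split only makes sense if DOR starts at response, so it shows which origin was intended.

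**Date arithmetic.** Let T0 be first dose, R first response, and E the event or censoring date.

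- DOR by the formula: E − T0 + 1
- DOR by the definition: E − R + 1
- Excess: R − T0
- TTR by the formula: R − T0 + 1, so the excess is TTR minus 1 day
- PFS by the formula: E − T0 + 1, so DOR equals PFS whenever the two share an event or censoring date

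**Per-patient results.** Response weeks are illustrations on the assessment grid. Progression is placed at the next scheduled assessment, 9 weeks later, which leaves room for the 4-week confirmation. Entries are days (months).

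| First response | Excess | Progression at | DOR by formula | DOR by definition |
|---|---|---|---|---|
| Week 9 | 63 (2.1) | Week 18 | 127 (4.2) | 64 (2.1) |
| Week 18 | 126 (4.1) | Week 27 | 190 (6.2) | 64 (2.1) |
| Week 27 | 189 (6.2) | Week 36 | 253 (8.3) | 64 (2.1) |

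The last two patients have responses of about 2 months, yet both would count in the 6-month category.

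**Ongoing responders censored at week 57.** The formula gives 57 × 7 + 1 = 400 days (13.1 months) whenever the response began. The definition gives 337 days (11.1) for onset at week 9, 274 (9.0) at week 18 and 211 (6.9) at week 27. All three would pass the 12-month threshold by the formula, and none by the definition.

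**Effect on summaries, under assumptions.** Suppose onset is at weeks 9, 18 and 27 in 60%, 30% and 10% of responders, true DOR is exponential with median m, and there is no censoring. The offsets are 2.07, 4.14 and 6.21 months. Beyond 6.21 months the survival function of the formula-based DOR is 2^(−t/m) × K, where K = 0.6 × 2^(2.07/m) + 0.3 × 2^(4.14/m) + 0.1 × 2^(6.21/m). The median is therefore m × (1 + log2 K).

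- m = 6.0: K = 0.762 + 0.484 + 0.205 = 1.451, so the median is 6.0 × 1.537 = 9.2 months.
- m = 9.5: K = 0.698 + 0.406 + 0.157 = 1.261, so the median is 9.5 × 1.335 = 12.7 months.

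For DOR of at least 6 months, a week-27 responder always qualifies because the offset alone exceeds 6 months.

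- m = 6.0: 0.6 × 2^(−3.93/6) + 0.3 × 2^(−1.86/6) + 0.1 = 0.72, against a true 0.50.
- m = 9.5: 0.6 × 2^(−3.93/9.5) + 0.3 × 2^(−1.86/9.5) + 0.1 = 0.81, against a true 0.65.

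A simulation of 400,000 responders gave the same four results.

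**The case against.** The best reply is that the SAP defines DOR correctly in words in the same section, and that the closing line is a generic day-count convention. A careful programmer would follow the specific definition. The protocol (section 10) and the SAP (sections 5 and 8) count follow-up for DOR from the start of response, so the intended origin is clear. DOR values identical to PFS among responders would probably be noticed. DOR is a secondary endpoint without a hypothesis test, and the success rule does not depend on it. The onset mix and the exponential durations are assumptions, not trial figures.

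Much of this is fair. The overstatement occurs only if the formula is programmed as written, and the modelled medians only illustrate its size. But the formula is the only calculation rule the SAP gives, and it says it covers every variable above it. The DOR paragraph also contains a second trace of first-dose logic: a censoring rule at first study treatment, repeated under PFS, for patients with no evaluable post-baseline assessment. A plan meant to fix the analysis before database lock should not leave two DOR values available for each responder and rely on someone noticing.

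A further point concerns patients deemed PR because surgery became possible with clear margins (SAP 4.4.1, protocol 7.7.2). They may have no date on which measurement criteria were met. That gap already exists in the SAP's own DOR definition and is not created by the correction.

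**Conclusion.** The concern holds. The formula in SAP 4.4.2 contradicts the DOR definition in the same section and is wrong for DOR as written. If it is applied, each responder's DOR is too long by the elapsed time from first dose to first response. That is about 2 months for a response at the first scheduled assessment, 4.1 months at week 18 and 6.2 months at week 27. These offsets are plain date arithmetic on the protocol schedule. The shifts in the median (6.0 to 9.2 months, 9.5 to 12.7) and in the proportion lasting at least 6 months (50% to 72%, 65% to 81%) rest on the assumed onset mix, exponential durations and no censoring. ORR, its confidence interval, the sample size, PFS, OS and TTR are not affected. Because DOR carries so much weight in this single-arm trial and the correction is so small, it must be made before database lock.

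**What to change.** In SAP 4.4.2:

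1. Limit the existing formula to PFS, OS and TTR.
2. Add: *DOR (day) = date of progression, death or censoring − date of first documented CR or PR (later confirmed) + 1.*
3. Delete the DOR bullet that censors at first study treatment. SAP 4.4.1 requires a CR or PR to be confirmed by consecutive evaluations at least 4 weeks apart, so a responder by measurement always has evaluable post-baseline assessments. Censoring at first dose would also precede the response.
4. While the text is open, state which date starts DOR for a patient deemed PR through surgery.

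The cost is a few lines of SAP text and the matching program specification. No data collection, sample size or primary analysis changes. Reported DOR will be shorter than the formula as written would give.

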1.4.3 Exploratory Efficacy Variables

The following exploratory efficacy variables will be analyzed.

- Association between efficacy and PD-L1 level
- Association between efficacy and TMB

4.5. Safety Variables

Patient safety will be assessed through the collection of reported adverse events (AEs), clinical laboratory data, vital signs, ECG and physical exam. Unless otherwise noted, the baseline value is defined as the last available value before the first dose of study treatment.

4.5.1. Adverse Events and Serious Adverse Events

The investigator (or designee) will seek information on AEs at each patient contact, and record all AEs that occur from the time the informed consent is signed until 105 days after the last dose of study drug. Prior to initiation of study drug, only the following categories of AEs should be reported on the AE CRF:

- SAEs
- Non-SAEs associated with a protocol-mandated intervention (eg, AEs related to an invasive procedure such as a biopsy)

Other AEs that occur prior to first treatment should be reported on the medical history CRF.

All AEs after initiation of study treatment and until 105 days after the last dose of study treatment, regardless of relationship to study treatment, will be reported on the AE CRF. Additionally, any SAE or AE that the investigator believes may be related to study drug and that occurs later than 105 days after last dose of study drug should be reported.

All adverse events are to be coded to a Preferred Term (PT) and associated primary System Organ Class (SOC) according to the latest available version of Medical Dictionary for Regulatory Activities (MedDRA).

An Adverse Event (AE) is any untoward medical occurrence in a patient or clinical investigation patient administered a pharmaceutical product and which does not necessarily have to have a causal relationship with this treatment. A Serious Adverse Event (SAE) is an AE that is classified as serious according to the criteria specified in the protocol.

The severity of AEs (including test findings classified as AEs) will be graded using the current version of the National Cancer Institute-Common Terminology Criteria for Adverse Events (NCI-CTCAE) grading system. Adverse events not listed in the NCI-CTCAE will be graded according to the following scale:

1. (Mild): Mild; asymptomatic or mild symptoms; clinical or diagnostic observations only; intervention not indicated.
2. (Moderate): Moderate; minimal, local or noninvasive intervention indicated; limiting age-appropriate instrumental ADL*.
3. (Severe): Severe or medically significant but not immediately life-threatening; hospitalization or prolongation of hospitalization indicated; disabling; limiting self-care ADL**.
4. (Life-threatening): Life-threatening consequences; urgent intervention indicated.
5. (Death): Death related to AE.

* Instrumental Activities of Daily Living (ADL) refer to preparing meals, shopping for groceries or clothes, using the telephone, managing money, etc.

** Self-care ADL refer to bathing, dressing and undressing, feeding self, using the toilet, taking medications, and not bedridden.

The relationship of AEs to study drug will be assessed by the investigator and be determined based on protocol specified criteria.

Laboratory results, vital signs, or ECG abnormalities are to be recorded as AEs if they are medically relevant: symptomatic, requiring corrective therapy, leading to treatment discontinuation and/or fulfilling a seriousness criterion.

4.5.2. Adverse Events of Special Interest

An AE of special interest (AESI) must be reported within 24 hours of identification. AEs of special interest for this study include:

- Grade 2 or greater infusion-related reactions
- Grade 2 or greater allergic/hypersensitivity reactions
- Grade 3 or greater immune-related toxicities (irAE)
- An irAE of any grade in a patient previously treated with a PI 3-K inhibitor.

Potential irAEs and Identified irAEs: Treatment-related TEAEs from the [Sponsor Master List of Immune-Related PTs](#) will be considered potential irAEs. From the potential irAEs, the sponsor created a subsequent case definition for identified irAEs, defined as potential irAEs requiring treatment with corticosteroid or immunosuppressant, or potential irAEs that are immune-related endocrinopathies.

4.5.3. Laboratory Safety Variables

The clinical laboratory data consists of serum chemistry, hematology, and urinalysis. Clinical laboratory values will be converted to standard international (SI) units and grouped by function in summary tables. Conventional unit may be provided. Functions are defined as follows:

Blood Chemistry: Sodium; Potassium; Chloride; Carbon dioxide (bicarbonate); Calcium; Glucose; Albumin; Creatinine; Blood urea nitrogen (BUN); Urea; Aspartate aminotransferase (AST); Alanine aminotransferase (ALT); Alkaline phosphatase (ALP); Total bilirubin; Creatine phosphokinase (CPK)

Hematology: Hemoglobin; White blood cells (WBCs); Platelet count; Differential: Neutrophils, Lymphocytes, Monocytes

Urinalysis: Glucose; pH; Ketones; Blood; Specific gravity; Spot urine protein

4.5.4. Vital Signs

Vital signs will be collected according to Table 4, Table 5, and Table 6 of the protocol: Body temperature (°C); Resting systolic blood pressure and diastolic blood pressure (mmHg); Pulse (beats/minute); Respiratory rate (breaths/minute)

4.5.5. 12-Lead Electrocardiography (ECG)

A standard 12-lead ECG will be performed at time points according to Table 4, Table 5, and Table 6 of the protocol. On treatment days, ECG will be collected 30 minutes (± 10 minutes) after the end of the infusion. The ECG strips or reports will be retained with the source. The ECG will be reviewed by the investigator (paper or electronic tracing) and will be available for comparison with subsequent ECGs by the investigator: PR Interval (msec); QRS Interval (msec); QT Interval (msec); Heart Rate (beat per minute; recorded from the ventricular rate)

Any ECG finding that is judged by the investigator as a clinically significant change (worsening) compared to the baseline value will be considered an AE, recorded, and monitored.

4.5.6. Physical Examination Variables

A thorough complete or limited physical examination will be performed at visits specified in Table 4, Table 5, and Table 6 of the protocol. Care should be taken to examine and assess any abnormalities that may be present, as indicated by the patient's medical history.

Complete physical examination will include examination of head and neck, lungs, heart, abdomen, lymph nodes, extremities, and skin, as well as a brief neurologic examination. Limited physical examination will include lungs, heart, abdomen, and skin.

4.6. Pharmacokinetic Variables and Anti-Drug Antibody Variables (ADA)

4.6.1. Pharmacokinetic Variables

Serum concentration of cemiplimab will be assessed at multiple time points throughout the study treatment and follow-up periods, and descriptive PK variables will include:

- C_{trough} – pre-infusion concentration
- C_{eoi} – concentration at end-of-infusion
- t_{eoi} – time of end-of-infusion

4.6.2. Immunogenicity Variables

The immunogenicity variables are ADA status, titer, NAb status, and time-point/visit. Serum samples for ADA will be collected at the clinic visits specified in the table of events (Table 4, Table 5, and Table 6).

5. STATISTICAL METHODS

For continuous variables, descriptive statistics will include the following: the number of patients reflected in the calculation (n), mean, median, standard deviation, minimum, and maximum. In addition, 25th percentile and 75th percentile will be provided.

For categorical or ordinal data, frequencies and percentages will be displayed for each category. The denominator will be determined by the analysis population used for the summary.

For time-to-event variables, median time-to-event (and the survival rate at a fixed time point) and its two-sided 95% confidence intervals will be summarized by the Kaplan-Meier method, unless otherwise specified.

Statistical analysis for efficacy in Group 1 and Group 2 will be conducted independently.

In order to describe ORR and DOR, the data cut for primary efficacy analysis will allow responding patients to be followed from onset of response for at least 6 months. For primary analysis, the last patient in a group will have the opportunity to be followed for approximately 57 weeks, including 27 weeks (cycles 1 to 3) for response, plus an additional 30 weeks (cycles 4 to 6) for DOR. If the last patient(s) has early EOS, the timing of data cut will be determined by the enrollment date of the last enrolled patient who remains on study (first dose + approximately 57 weeks).

An interim analysis of Group 1 patients will be performed at the time of the primary analysis for Group 2. For additional details, please see Section 8.

An updated analysis of the response duration will be performed after all responding patients have been followed for a minimum of 12 months from onset of response.

5.1. Demographics and Baseline Characteristics

Patient demographics and baseline characteristics variables listed in Section 4.1 will be listed and summarized by group and combined. Reasons for Group 2 patients not being candidate for surgery or radiation will be listed and summarized.

Assessments made before the first dose of cemiplimab will be used as baseline measurements for the purposes of statistical analysis and reporting unless otherwise specified.

5.2. Medical History

Medical history will be listed and summarized by group and combined. Listing of medical history will include SOC, PT, investigator verbatim and start and end dates. Medical history will be summarized by SOC and PT and will be sorted by decreasing frequency of SOC followed by PT.

5.3. Prior/Concomitant Medications and Procedures

Prior medications and procedures will be listed and summarized by group and combined. Listing of prior cancer related medications will include generic name, ATC levels 2 and 4, start and end dates. Listing of prior cancer related radiotherapy will include type of radiation therapy, site of radiation, intent of treatment, start and end dates, and total dose. Listing of prior cancer related surgery will include type of procedure, date of surgery, and surgery location. The number and percentage of patients who received any prior cancer related medications, prior cancer related radiotherapy, or prior cancer related surgery will be summarized. The number and percentage of

patients who received any prior HHI therapy will also be summarized. Reasons for discontinuation of prior HHI therapy will also be listed and summarized.

Concomitant medications and procedures will be listed and summarized by group and combined. Listing of concomitant medications will include generic name, ATC levels 2 and 4, indication, start and end dates, dose, route, frequency, and ongoing status. Concomitant medications will be summarized by ATC level 2 and ATC level 4. Concomitant procedures will be summarized by SOC and PT.

Post treatment anti-tumort therapy will be listed.

